5.4. Analysis of Central Tendency (By-timepoint Analysis)

By-timepoint analysis will be performed using Holter ECG data from subjects in the Holter ECG Analysis Population. Absolute values, change-from-baseline and time-matched, placebo-corrected, change-from-baseline values for each ECG parameter will be considered for this analysis (Refer to DMID 16-0110_ECG_Table shells: Tables 3, 4 and 5; DMID 16-0110_ECG_Listing shells: Listings 1 to 7; DMID 16-0110_ECG_Figure shells: Figure 1 to 56). Change-from-baseline QTcF (Δ QTcF) values (and other ECG parameters QTcB, HR

[calculated from RR], RR, QT, PR and QRS duration values) will be calculated by subtracting the mean value of replicate ECGs at baseline from the mean value of replicate ECGs at post-dose timepoints.

Time-matched, placebo-corrected, change from baseline in QTcF interval ($\Delta\Delta\text{QTcF}$) values (and other ECG parameters QTcB, HR [calculated from RR], RR, QT, PR and QRS duration values) will be calculated as differences between time-matched change-from-baseline QTcF values for active treatment minus time-matched change-from-baseline QTcF values for placebo for each subject (Refer to DMID 16-0110_ECG_Table shells: Table 5; DMID 16-0110_ECG_Listing shells: Listings 1 to 7).

As a primary analysis, a repeated measurement analysis on $\Delta\Delta\text{QTcF}$ values will be performed at each post-dose timepoint using analysis of covariance (ANCOVA) (Refer to DMID 16-0110_ECG_Table shells: Table 6; DMID 16-0110_ECG_Figure shells: Figure 57). Unless otherwise specified, a restricted maximum likelihood based, linear mixed effect model will be used. Model will include $\Delta\Delta\text{QTcF}$ as the dependent variable. Baseline QTcF value as continuous covariate and sequence, period, treatment, nominal timepoint (as categorical) and interactions of timepoint with treatment will be treated as fixed effects. The model will also include subject nested within sequence as a random effect. SAS PROC MIXED will be used to perform the analysis.

At each of the 9 post-dose timepoints and for each zoliflodacin dose, a one-sided 95% CI for the treatment effect on $\Delta\Delta\text{QTcF}$ will be estimated using least square (LS) means. There will be 18 CIs, one for each combination of zoliflodacin dose and timepoint. A negative effect of 2 g or 4 g zoliflodacin will be concluded if the maximum of the 18 one-sided 95% CI upper bounds is <10 msec. No adjustment will be made for multiplicity.

SAS code will be similar to:

```
PROC MIXED;
  CLASS TREATMENT PERIOD SEQUENCE TIME SUBJ;
  MODEL   $\Delta\Delta\text{QTcF}$  = TREATMENT PERIOD SEQUENCE TIME BASELINE_QTCF
  TIME*TREATMENT;
  RANDOM SUBJECT(SEQUENCE);
  REPEATED TIME / SUBJ=SUBJ(PERIOD) TYPE=CS;
  LSMEANS TIME*TREATMENT / ALPHA=0.1;
RUN;
```

In the above model, treatment will be Zoliflodacin 2 g and Zoliflodacin 4 g.

Similar ANCOVA models will also be done for QTcB, HR (calculated from RR), RR, QT, PR and QRS as secondary analyses (Refer to DMID 16-0110_ECG_Table shells: Table 6; DMID 16-0110_ECG_Figure shells: Figure 57 to 63).

The analysis will also be presented in graphs. For each of the 2 active treatments, all 9 confidence intervals (corresponding to the 9 post-dose timepoints) will be presented on one graph. The change from baseline (ΔQTcF) and placebo-corrected change from baseline QTcF ($\Delta\Delta\text{QTcF}$) will be presented separately (Refer to DMID 16-0110_ECG_Figure shells: Figure 57 to 63).

Assay sensitivity (i.e., the ability to detect small increases from baseline QTcF duration) will be established by comparing the time-matched placebo-corrected change from baseline in QTcF in the moxifloxacin at the following 4 timepoints, i.e., 1, 2, 3, and 4 hours post-dose. The model as described in the primary analyses will be used. If the lower bound of one-sided 95% CI for treatment effect on $\Delta\Delta\text{QTcF}$ in at least one timepoint is >5 msec, it will be concluded that the assay is sensitive to small increases in baseline QTcF duration. Multiplicity adjustment will be done using the Bonferroni correction method. Since 4 timepoints and overall two-sided alpha of 0.1 are included in the analysis, two-sided alpha will be set to $0.1/4 = 0.025$ in the model (Refer to DMID 16-0110_ECG_Figure shells: Figures 64 and 65).

```
PROC MIXED;
  CLASS PERIOD SEQUENCE TIME SUBJ;
  MODEL  $\Delta\Delta\text{QTcF}$  = PERIOD SEQUENCE TIME BASELINE_QTcF;
  RANDOM SUBJECT (SEQUENCE);
  REPEATED TIME / SUBJ=SUBJ (PERIOD) TYPE=CS;
  LSMEANS TIME / ALPHA=0.025;
RUN;
```

In addition, using the above linear mixed effects model, least squares mean estimates of $\Delta\Delta\text{QTcF}$ and their one-sided 95% CIs for moxifloxacin will be obtained for the treatment effect at all post-dose timepoints without multiplicity correction and displayed graphically to demonstrate the time course of the moxifloxacin effect.

Descriptive statistics (number of subjects, mean, SD, median, CV, minimum, maximum, SE and one-sided 95% CI) will be used to summarize the ECG parameters for each timepoint and for each treatment. For those visits with $N \leq 3$, only median, maximum, and minimum values will be provided. These will be provided for absolute values and change from baseline values for all 4 treatments. Time-matched, placebo-corrected, change from baseline values will be provided for the 2 g zoliflodacin, 4 g zoliflodacin, and moxifloxacin for QTcF, QTcB, HR (calculated from RR), RR, QT interval, PR interval, and QRS duration.

Descriptive statistics will also be shown graphically with the x-axis showing the nominal time and the y-axis showing the mean change from baseline and its one-sided 95% CI for each of the ECG intervals parameters separately (i.e., QTcF, QTcB, HR, RR, QT, PR and QRS) for each of the treatment periods.

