5.3.4 Handling of Withdrawals and Discontinuation of Administration

- Subjects who are withdrawn before dosing may be replaced with a subject assigned the same sequence.
- A subject who cannot ingest the entire 60 mL volume of zoliflodacin or placebo suspension or a subject who took the entire dose but vomits up to 5 h after dosing with zoliflodacin or placebo or moxifloxacin will be withdrawn from data analysis for the period when the event occurred, but will not be withdrawn from the trial and may complete the remaining treatment periods in the assigned dosing sequence.
- Subjects who ingest the entire volume of the initial 60-mL drug suspension but who do not ingest the content of the second 60-mL rinse will not be withdrawn from the trial.
- Subjects who withdraw after receiving at least one treatment in a treatment sequence will not be replaced, unless more than 16 subjects withdraw from the trial.
- Subjects who received any amount of the study drug but withdraw from the trial within 24 h after dosing will be encouraged to continue follow-up (with subjects' consent) for safety assessments and PK sample collection.
- Subjects withdrawing will be asked to complete an ET Visit if they do not wish to be followed per protocol.

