11.4.5 Missing Values and Outliers

All attempts will be made to collect all data per protocol. No imputation will be performed for missing values. Outliers will not be excluded from the primary analyses. Outliers identified during the PK analysis will be discussed in the analysis report.

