11.4.6 Analysis of Continuous ECG Parameters (Pharmacodynamics)

11.4.6.1 ECG Analysis and Interpretation

The $\Delta\Delta\text{QTcF}$, calculated as differences between time-matched mean change-from-baseline QTcF values for active treatment relative to placebo, will be evaluated to quantify the QTcF prolongation of the active treatments. The median of the three Holter ECG QTcF interval measurements at 45, 30, and 15 min before each dosing will be regarded as baseline for the respective period.

QTcF corrections will be calculated using Fridericia's formula:

- $\text{QTcF} = \text{QT} / \text{RR}^{0.33}$

The primary variable will be the change-from-baseline QTcF (ΔQTcF). Other endpoints to be evaluated include HR (bpm; calculated from RR interval measurements), PR (msec), QRS (msec), RR (msec), and cardiac abnormalities (morphologies, rhythm, and conduction).

All statistical analyses and reporting of digital ECG data will be conducted on the mean of the replicate intervals within a timepoint. Descriptive statistics including two-sided 90% CI will be generated for observed, change-from-baseline, and time-matched placebo-corrected change-from-baseline ECG intervals.

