11.4.6.2 Primary Analysis: QTcF Effect

The primary hypothesis to be tested is that following administration of zoliflodacin 2 g and 4 g, the upper bound of the one-sided 95% CI of treatment effect on $\Delta\Delta\text{QTcF}$ is ≥ 10 msec for at least one of the ECG assessments, against the alternative hypothesis that all mean effects are < 10 msec.

The primary analyses will be conducted to evaluate the effects of zoliflodacin 2 g and 4 g on cardiac repolarization as measured by ΔQTcF relative to placebo. Analysis will be performed using a linear mixed model with $\Delta\Delta\text{QTcF}$ as the dependent variable, with baseline QTcF, sequence, period, treatment, time (categorical), and interactions of time with treatment as fixed

effects, and subject nested within sequence as random effects. At each of the 9 post-baseline timepoints and for each zoliflodacin dose, a one-sided 95% CI for the treatment effect on $\Delta\Delta\text{QTcF}$ will be estimated using least square means. There will be 18 CIs, one for each combination of zoliflodacin dose and timepoint. A negative effect of 2 g or 4 g zoliflodacin will be concluded if the maximum of the 18 one-sided 95% CI upper bound is <10 msec. No adjustment will be made for multiplicity, since it is not required under intersection-union testing, as planned for the trial. No subgroup analyses are planned.

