6.5. Missing Data

No imputation of missing data is planned.

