5.5. Pharmacokinetic-QTcF Analysis

PK-QTcF analysis will be performed using individual PK and $\Delta\Delta\text{QTcF}$ data from all timepoints from all subjects regardless of dose of zoliflodacin, in the PK-ECG Analysis Population. Time-matched plasma concentration of zoliflodacin and corresponding $\Delta\Delta\text{QTcF}$ data will be used to quantify the relationship between exposure and response ($\Delta\Delta\text{QTcF}$). Moxifloxacin will not be included in this analysis. A linear or nonlinear mixed effects modeling approach will be used to quantify the relationship between plasma concentration of zoliflodacin and $\Delta\Delta\text{QTcF}$ (Refer to DMID 16-0110_ECG_Table shells: Tables 12 to 15; DMID 16-0110_ECG_Listing shells: Listings 16 and 17; DMID 16-0110_ECG_Figure shells: Figure 66 to 71).

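### Within-subject ΔΔQTcF as the modelled response discards the active data of any subject without a usable placebo period; a four-treatment ΔQTcF model would keep them

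*SAP*

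**What the plan says.** Protocol 11.4.6.1 states: "The primary variable will be the change-from-baseline QTcF". Protocol 11.4.6.2 describes the effect as ΔQTcF relative to placebo, but then takes ΔΔQTcF "as the dependent variable, with baseline QTcF, sequence, period, treatment, time (categorical), and interactions of time with treatment as fixed" effects.

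ECG SAP 5.4 follows the second reading. ΔΔQTcF is "calculated as differences between time-matched change-from-baseline QTcF values for active treatment minus time-matched change-from-baseline QTcF values for placebo for each subject", and it is the dependent variable. Under the SAS code the SAP adds: "In the above model, treatment will be Zoliflodacin 2 g and Zoliflodacin 4 g". The assay-sensitivity model uses the same response for moxifloxacin. In ECG SAP 5.5, time-matched concentrations and ΔΔQTcF "will be used to quantify the relationship between exposure and response".

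On missing data, the protocol (11.4.5) says "No imputation will be performed for missing values" and the SAP (6.5) says "No imputation of missing data is planned". Under Protocol 5.3.4, up to 16 subjects who withdraw after dosing are not replaced. A subject who vomits or cannot take the full dose, placebo included, "will be withdrawn from data analysis for the period when the event occurred, but will not be withdrawn from the trial".

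**The concern.** ΔΔQTcF exists only where the same subject has both an active and a placebo value at that timepoint. A subject who leaves before the placebo period, or whose placebo period is excluded, has no row in any of the three models. Those active data still appear in the ΔQTcF summaries for all four treatments, the outlier tables and the safety tables. One missing placebo ECG has the same effect at a single timepoint.

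Two things are at stake: precision that the collected data could have given, and possible selection. A QTcF rise of 60 msec or more is Grade 3 (Protocol Appendix C, Table 9), and a Grade 3 event judged related leads to withdrawal (Protocol 7.3). Protocol 5.3.3 also lists such a rise as a possible reason for removal. The 4 g dose precedes placebo in 6 of the 12 sequences. A high responder removed at that point would be missing from all 18 bounds, which favours a negative study.

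**Working it through.** **1. The plan's own figure.** Inputs from Protocol 11.2 and 11.4.6.2: SD of ΔΔQTcF 7 msec, true effect 5, margin 10, n = 56, one-sided 5%.

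- SE = 7/√56 = 0.935. Power per bound (noncentral t, 55 df) is 0.99986. For 9 independent bounds it is 0.9987, and for 18 it is 0.9975. So at least 84% is true but not tight.
- The nearest match takes 7 as the SD of ΔQTcF per treatment. The SD of the difference is then 7√2 = 9.9, power per bound 0.9816, and 0.9816⁹ = 0.846. The documents attach 7 msec to ΔΔQTcF, so 9.9 is an assumption. Both values are carried below.

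**2. Data lost.** Placebo falls in each period in 3 of 12 sequences. A subject leaving after period k has had no placebo with probability 1 − k/4, and then loses k active periods. Assume 16/3 withdrawals after each of periods 1, 2 and 3.

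- Subjects lost: 16/3 × (0.75 + 0.50 + 0.25) = 8.
- Active periods lost: 16/3 × (0.75 + 1 + 0.75) = 13.3.
- Active periods observed: 56 × 3 + 16/3 × (0.75 + 1.5 + 2.25) = 192. The loss is 7%, or 4.4 of 64 per active arm.
- PK-QTcF: 8.9 of 128 zoliflodacin periods; × 9 timepoints, 80 of 1,152 pairs.

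**3. Standard error of the 4 g contrast at SD 7.** For ΔΔQTcF, SE = 7/√(number of pairs). For the four-treatment model, generalised least squares was used with period and treatment fixed, subject random and residual variance 49/2. The within-subject correlation of ΔQTcF is not documented, so it was varied from 0 to 0.5. Means over 400 random withdrawal patterns:

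| Timing of the 16 withdrawals | ΔΔQTcF | Four-treatment ΔQTcF |
|---|---|---|
| None | 0.825 | 0.825 |
| Evenly after periods 1–3 | 0.909 | 0.878–0.889 |
| All after period 1 | 0.935 | 0.905–0.921 |
| All after period 2 | 0.914 | 0.876–0.889 |
| All after period 3 | 0.874 | 0.849–0.855 |

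For even withdrawal the ratio is 1.02 to 1.035. Other variance structures, with a subject-by-period component and larger subject variance, give up to about 1.045. On a bound, 1.645 × (0.912 − 0.883) = 0.05 msec. The moxifloxacin SE is about 3% larger.

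**4. Placebo periods excluded in completers (illustration; no rate is documented).** Each takes out 3 active periods. One, 4 or 8 such subjects raise the 4 g SE by 0.35%, 1.4% or 3%. With 16 withdrawals plus 3 exclusions, about 22 of 191 active periods (12%) are lost and the SE is about 4 to 6% larger.

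**5. Joint power for all 18 bounds.** Assumptions: 5 msec at every time and both doses, 16 even withdrawals, SE 0.912 against 0.883 (× √2 for SD 9.9), correlation between doses 0.5.

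| SD | Time correlation | ΔΔQTcF | ΔQTcF |
|---|---|---|---|
| 7 | 0 to 0.7 | 99.87–99.91% | 99.94–99.95% |
| 9.9 | 0 | 79.4% | 84.6% |
| 9.9 | 0.4 | 84.2% | 88.0% |
| 9.9 | 0.7 | 89.2% | 91.7% |

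**6. Selection.** A 60 msec rise lies 55 msec above a 5 msec mean. That is 55/9.9 = 5.6 to 55/4.95 = 11.1 SD of ΔQTcF for SDs from 9.9 down to 4.95 (7/√2), so practically never under the plan's assumptions. Keeping one such subject in the four-treatment model would move the 4 g estimate by 0.04 to 0.76 msec, depending on sequence, time of withdrawal and how many timepoints are affected.

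**The case against.** The strongest reply is that the plan has already paid for this loss. It is sized on ΔΔQTcF with 56 evaluable subjects, and even withdrawal leaves 64 − 4.4 = 59.6 pairs per arm. Even with three placebo exclusions added, the SE is 0.936, practically the planned 0.935. That stands: the ΔΔQTcF model meets its own precision target in these scenarios. The visible power gain needs an SD of 9.9, which the documents do not state. That also stands.

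The selection route is rare. Removal under Protocol 5.3.3 is discretionary, the Grade 3 route needs a relatedness judgement, and the grading and halting rules appear to use standard 12-lead ECGs, not Holter values. It supports the change but does not carry it.

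ECG SAP 5.2 tabulates expected and missing ECGs, and section 5.4 gives N for both ΔQTcF and ΔΔQTcF, so the size of the drop can be read off. Neither brings the data back into a bound.

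The four-treatment model relies on a random subject effect and one covariance structure for all four treatments. That is a real assumption and should be stated. With complete data both approaches give the same SE.

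Finally, ΔΔQTcF can be called a deliberate choice: Protocol 11.4.6.2, the protocol's PD population and the ECG SAP agree on it. Even so, Protocol 11.4.6.1 names a different primary variable and needs to be reconciled.

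**Conclusion.** The concern holds. As written, observed active data without a matching placebo period are left out of all three decision analyses, and no other provision restores them. With the permitted 16 withdrawals spread evenly, about 7% of active periods are lost and the 4 g SE is 2 to 4.5% larger than necessary. The range reflects the undocumented correlation structure. At SD 7 this changes no decision. At SD 9.9 it costs about 2.5 to 5 points of joint power. The change is worth making because it keeps the estimand, uses data already collected, costs no precision when data are complete, and removes a loss that, in the rare selective case, would favour a negative result.

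**What to change.** Reconcile Protocol 11.4.6.1 with 11.4.6.2, and fit one mixed model to ΔQTcF:

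- **Fixed effects:** treatment (four levels, placebo included), time, treatment-by-time, period, sequence, and that period's own baseline.
- **Covariance:** random subject within sequence, repeated time within subject-period, Kenward-Roger degrees of freedom.
- **Contrasts:** ΔΔQTcF as the least-squares mean difference from placebo at each time (ALPHA=0.1), with the moxifloxacin contrasts at 1 to 4 h from the same fit (ALPHA=0.025).
- **Unchanged:** the 10 msec margin and the 18-bound rule.

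In ECG SAP 5.5, state how active data without placebo are handled: either model ΔQTcF with the placebo rows included, or drop those pairs and report how many.

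The cost is a short amendment of Protocol 11.4.6.1 and 11.4.6.2, edits to ECG SAP 5.4 and 5.5 before unblinding, and a few lines of SAS. No new data are needed.

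If ΔΔQTcF stays primary, prespecify the ΔQTcF model as a sensitivity analysis and list every subject-period with active data but no ΔΔQTcF, with the reason. That needs SAP text only.

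Three small points can be tidied at the same time, with no effect on the bounds: the differing population definitions (Protocol 11.4.1 against ECG SAP 4), which baseline is the covariate, and PERIOD being aliased with SEQUENCE in the moxifloxacin code.

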5.4.1. Categorical analysis

Categorical outlier analysis will supplement the central tendency analysis by determining if there were individual subjects who had an exaggerated effect on any ECG interval that were not revealed in a mean change from baseline central tendency analysis.

ECG parameter values from individual post-dose replicate ECGs at each timepoint (not mean or median of all replicates) will be considered separately for categorical outlier analysis.

Results of categorical outlier analysis will be presented as number and percentage of subjects in each treatment. Results will be tabulated by individual treatment. If a subject has more than one categorical outlier value for a parameter at a timepoint, then the subject will be counted only

once for that timepoint. Statistical tests for comparison between treatment arms will not be performed.

For outlier analysis, the baseline value for each participant is defined as mean of 3 pre-dose assessments (9 ECGs) on Day 1 (i.e. D1PRE45MIN, D1PRE30MIN and D1PRE15MIN) of the corresponding treatment period.

ECG parameters namely QT/QTc will be flagged as normal, abnormal insignificant or significant, based on the pre-approved study specific ECG abnormality criteria based on ICH E14 guidance.²

The categorical outlier values for QTcF, QTcB, HR, PR, and QRS parameters (**Refer to DMID 16-0110_ECG_Table shells: Table 9; DMID 16-0110_ECG_Listing shells: Listings 8 to 13**) for the individual subjects in each dose cohort will be summarized as follows:

1. QTcF and QTcB will be categorized using the following study-specific criteria:
 - QTc >450 msec to 480 msec
 - QTc >480 msec to 500 msec
 - QTc >500 msec
 - QTc increase from baseline ≥ 30 msec to <60 msec
 - QTc increase from baseline ≥ 60 msec
2. Uncorrected QT will be categorized for >500 msec.
3. Categorical outliers for HR (calculated from RR) will be categorized based on the following criteria:
 - HR change-from-baseline >25% decrease resulting in HR <50 bpm
 - HR change-from-baseline >25% increase resulting in HR >100 bpm
4. Categorical outliers for PR and QRS parameters will be categorized for the following criteria:
 - PR change-from-baseline >25% resulting in PR >200 msec
 - QRS change-from-baseline >25% resulting in QRS >120 msec

5.4.2. Analysis of ECG morphological abnormalities

The ECG morphological abnormalities will be presented in terms of the number and percentage of subjects in each treatment with changes from baseline that represent the appearance or the worsening of the morphological abnormality. The ECG morphological abnormalities will be summarized by treatment using the number and percentage of subjects within each treatment based on incidence rates. The denominator for the percentage will be the number of evaluable subjects in each treatment.

Abnormalities present in any one or more of the baseline timepoint replicate ECGs recorded for a particular period will be considered to be present at baseline for post-dose ECGs from that specific period.

If a subject has an ECG morphological abnormality in more than one replicate ECG of a study timepoint, the subject will be counted only once for that timepoint.

Morphological abnormalities will be summarized by treatment and by timepoint using the number and percentage of subjects within each treatment. No statistical test of significance will be applied. Treatment emergent morphological ECG abnormalities and their significance will be discussed in detail in the report.

T-wave morphology abnormalities will be presented separately in terms of the number and percentage of subjects in each treatment. The T-wave morphology abnormalities will be summarized by the T-wave morphology categories for abnormal T-waves such as flat T-waves, biphasic T-waves, and notched T-waves, as stated in section 8.3.1.2 of the protocol¹ (Refer to DMID 16-0110_ECG_Table shells: Tables 10 and 11; DMID 16-0110_ECG_Listing shells: Listings 14 and 15).

